## MEASURES

Data collected will include (1) adolescent and parent demographic characteristics, (2) vaccine completion, and (3) parent and adolescent individual interviews.

**Demographic Characteristics (Aim 1).** The adolescent's age, sex, race/ethnicity, insurance type, area deprivation index for residence, and distance from clinic will be obtained from EHR data and recorded on data collection forms. Adolescent's insurance type will be determined by the parent's insurance provider listed in the chart. Area deprivation index for residence, determined by the parent household where the adolescent lives, will be measured using zip codes and linked by subject ID number with the area deprivation index public database to determine the index value for their place of residence. This index value is assigned to neighborhoods using 9-digit zip codes and identifies the percentage of the population that experiences socioeconomic deprivation within a neighborhood in a given geographic area based on the following variables: Education, median family income, employment, income disparity, housing units, federal poverty level, single-parent households, and household characteristics. Higher index values indicate higher levels of deprivation among a geographic area which has been associated with poorer health outcomes (University of Wisconsin Health Innovation Program, 2017). Distance from clinic will be calculated using the adolescent's address listed as the primary residence in their chart and measured as the number of miles from their place of residence to the pediatric clinic. The number of miles will be calculated using geographic information systems (GIS) software. All data will be used to describe the relationship between social determinants and vaccine completion. Parent or legal guardian characteristics including their age, sex, race/ethnicity, and relationship to the adolescent will also be collected to further describe the sample.

**Vaccine Completion (Aim 1).** Data on the number of HPV vaccine doses that the adolescent received within a 14-month period will be obtained from EHR data. In addition, the date of

vaccine administration and clinic location in which the vaccine doses were received will also be collected. The NCIR database will be used to determine vaccine doses received from clinics outside of the DUHS network for each subject. In the event that any of the HPV vaccine doses were received outside of the DUHS network, the clinic location in which the dose was received will be recorded. Vaccine completion will be operationalized as the receipt of 2 doses, as defined in the new vaccine administration guidelines for adolescents ages 11 to 14 years (Meites et al., 2016). Data on time to second dose and whether each dose was received during a well- or illness-visit will also be collected.

**Interviews (Aim 2).** Semi-structured, individual interviews will be conducted with parents and adolescents from the selected pediatric clinic. Parents and adolescents will participate in separate, concurrent interviews to maintain confidentiality and capture specific individual experiences with the HPV vaccine and barriers and facilitators to vaccination completion. Interviews will be conducted at one-time point with two members of the research team and last approximately 45 to 60 minutes. An interview guide for parents and adolescents will be used during interviews. Following interviews, demographic information will be collected from parents and adolescents to obtain descriptive data from participants.

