the area deprivation index of the adolescent's place of residence. Addresses will be recorded to calculate the number of miles for the distance from clinic variable. Lastly, the date of HPV vaccine administration will be used to determine the number of months between receipt of the first and second dose within a 14-month period. However, once area deprivation index values have been determined, the distance from clinic miles calculated using geographic information systems (GIS) software, and the date of vaccine administration have been converted to months (e.g. 1st dose = 1 month; 2nd dose = 8 months from first dose) participants' zip codes, addresses, and date of vaccine administration will be deleted from the dataset. Each eligible adolescents' chart will be provided with a subject ID number. To minimize the risk of loss of confidentiality, all data will be stored and secured in the PACE network. Additional data (i.e. analyses results) will be stored in an electronic, password-protected share drive at Duke University School of Nursing and will be backed up daily. Only the study team will have access to both the share drive and PACE network.

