**Risks:** To mitigate the potential risk for psychological distress related to discussion about cancer, sexual health, and the HPV vaccine, participants will be provided their rights to refuse answering questions during interviews that make them feel uncomfortable and withdraw from the study at any time as specified in the informed consent and child assent. Further, interviews will be scheduled at times convenient with participants' schedule (as specified by parents and adolescents) and at a private location of their preference (i.e. reserved room at Duke University campus or local library, home, etc.) to promote schedule flexibility and to make participants feel at ease during interviews. To minimize risks to children, assent will be obtained from each child which will describe their rights to participate in the study and refuse to answer questions that make them feel uncomfortable. The child's confidentiality will also be maintained through separate individual interviews away from their parents. The interviewer will promote open and honest communication with each participant to create a trusting environment. To protect confidentiality and prevent against a potential breach, each subjects' charts will be provided a participant ID number. Names and date of birth will not be recorded on data collection forms or used in qualitative interviews. All electronic data will be stored in a password protected share drive in which only study personnel will have access to. All hard copy forms (i.e. informed consent, child assent, and demographic surveys) will be stored in a locked file cabinet at DUSON. For aim 1, EHR data containing protected health information (i.e. addresses, zip codes, and date of vaccine administration) will be imported and stored in a secure folder in PACE and later removed from the dataset once area deprivation values and the number of miles from participants' place of residence to the selected pediatric clinic have been determined, and the date of vaccine administration has been converted to months. For aim 2, protected health information obtained for recruitment (e.g. names, addresses, phone numbers, and email addresses) will be recorded on a password-protected Excel document that will be stored in a secure folder within the study's shared drive and destroyed at the completion of data analysis. All collected information will be stored in a database on a standalone database server hosted by Duke Health Technology Services (DHTS). The database server resides behind the DHTS internal firewall and access to the server is controlled via firewall rules. All collected data is

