## **DATA ANALYSIS & STATISTICAL PLAN**

**Aim 1:** Descriptive statistics will be used to detail the characteristics and key measures for the eligible adolescents and their parents. Logistic regression will be used to determine the role that social determinants play in predicting HPV vaccine completion within 14 months. Individual-level determinants will be adolescent's age, sex, race/ethnicity, and insurance type; community-level determinants will be area deprivation index for residence and distance from clinic. Power calculations indicated a required sample size of 600 charts for adolescents who received the first dose of the HPV vaccine to achieve 80% power when conducting the primary analysis using multivariable logistic regression and supplemental regression analysis using Cox proportional regression models. This sample size estimate was based on the following assumptions: (a) up to 10 predictor terms in the final model; (b) medium effects, indicated by adjusted odds or hazards ratios; (c) two-tailed tests with significance set at 0.05 per test; and (d) an overall missing rate of less than 5% for terms in the model after imputation when needed. However, all charts that meet the eligibility criteria will be analyzed and it is estimated that the sample size will exceed the required sample size of 600 charts.

**Aim 2:** Directed qualitative content analysis will be conducted to examine parents and adolescents' experience with the HPV vaccine and barriers and facilitators to completing the vaccine series across level of determinant (e.g. individual, relationship, and community). For data integration, quantitative and qualitative data will be analyzed separately initially. Then, results from each separate analysis will be presented in data displays with an integrative summary for each level of determinant to assess patterns between quantitative and qualitative data and provide further description of the role that social determinants play on HPV vaccine completion.

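### The deprivation index is a neighbourhood-level value, but the plan names no method for clustering by neighbourhood and keeps no area code, so the index's standard error may be too small

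*Combined protocol and SAP*

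**What the plan says.** All references are to the Combined protocol and SAP.

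- **Level of the exposure.** MEASURES, Demographic Characteristics (Aim 1): "This index value is assigned to neighborhoods using 9-digit zip codes". Adolescents in the same neighbourhood therefore carry the same value.
- **Its role.** DATA ANALYSIS & STATISTICAL PLAN, Aim 1: "community-level determinants will be area deprivation index for residence and distance from clinic". H1 makes a directional prediction about it: lower completion where deprivation is high.
- **The models.** Same section: "Logistic regression will be used to determine the role that social determinants play in predicting HPV vaccine completion within 14 months", with "supplemental regression analysis using Cox proportional regression models". No random effect, frailty, estimating-equation approach or robust variance is named anywhere in the document.
- **The sample size.** Same section: "Power calculations indicated a required sample size of 600 charts for adolescents who received the first dose of the HPV vaccine". The stated target is 80% power. The listed assumptions are the number of predictor terms, a medium effect, two-sided 0.05 per test, and under 5% missing. There is no design effect or intraclass correlation.
- **The geographic identifiers.** DESIGN AND PROCEDURES, Procedures: Aim 1, says that after derivation the participants' "zip codes, addresses, and date of vaccine administration will be deleted from the dataset". RISK/BENEFIT ASSESSMENT repeats that they are "later removed from the dataset once area deprivation values and the number of miles" have been determined. Neither section mentions a coded area number that stays behind.

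**The concern.** Neighbours share the index value itself. They may also share schools, transport and local attitudes, none of which is in the model. A predictor that is constant within a group takes the whole design effect of any residual correlation within that group. Predictors that vary within the neighbourhood, such as age or sex, largely escape it. Ordinary logistic and Cox regression count each chart as separate evidence on the index, which overstates the information when such correlation exists.

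At stake is the deprivation part of H1: its confidence interval may be too narrow and its 5% test may reject too often. The timing also matters. The cleanest grouping variable, the neighbourhood itself, is removed under the plan's own privacy procedure, so an area code has to be provided for before that step is carried out.

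**Working it through.** **1. The plan's own figure.** The 600 charts can be neither reproduced nor refuted, because the odds ratio, completion rate and correlation among predictors are not given. The figure is attainable. For a continuous predictor, n = (z₀.₉₇₅ + z₀.₈₀)² / [P(1−P)(ln OR)²], divided by (1−R²) and by 0.95 for missing data. With assumed OR 1.3 per standard deviation, P = 0.5 and R² = 0.2:

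7.849 / (0.25 × 0.0688) = 456; 456 / 0.8 = 570; 570 / 0.95 gives 601 after rounding up.

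This calculation takes all charts as independent.

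**2. Design effect for a predictor constant within area.** Let m be adolescents per area and ρ the residual intraclass correlation. Both are assumptions.

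- Design effect: DE = 1 + (m−1)ρ
- True standard error = model-based standard error × √DE
- True type I error = 2[1 − Φ(1.96/√DE)]
- Charts needed = 600 × DE
- Power at 600 with a corrected standard error = Φ[(1.96 + 0.84)/√DE − 1.96]

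| m | ρ | DE | √DE | Type I error | Charts needed | Power at 600 |
|---|---|---|---|---|---|---|
| 2 | 0.02 | 1.02 | 1.010 | 0.052 | 612 | 79.2% |
| 2 | 0.05 | 1.05 | 1.025 | 0.056 | 630 | 78.1% |
| 5 | 0.02 | 1.08 | 1.039 | 0.059 | 648 | 76.9% |
| 5 | 0.05 | 1.20 | 1.095 | 0.074 | 720 | 72.5% |
| 10 | 0.02 | 1.18 | 1.086 | 0.071 | 708 | 73.2% |
| 10 | 0.05 | 1.45 | 1.204 | 0.104 | 870 | 64.3% |

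With ρ = 0, or m close to 1, nothing changes.

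**3. Simulation.** 600 charts, no true index effect, 1,000 data sets per setting, ordinary logistic standard error, nominal 0.05. Monte Carlo error is about ±0.014 near 0.05.

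| Adolescents per area | ρ = 0.02 | ρ = 0.05 |
|---|---|---|
| about 3 | 0.053 | 0.061 |
| 6 | 0.050 | 0.099 |
| 15 | 0.061 | 0.109 |

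At ρ = 0 the rate was 0.046 to 0.048, as it should be.

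Formula and simulation do not agree cell by cell. At m = 15 and ρ = 0.05 the formula gives DE = 1 + 14 × 0.05 = 1.70, √DE = 1.304 and a type I error of 0.133, against 0.109 simulated. The formula is a large-sample approximation with equal areas, so I rest the conclusion on the simulated range and read it only as an order of magnitude.

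**4. Can it be repaired after deletion?** The index value stays in the file as a predictor. Everyone in a neighbourhood has the same value, so groups defined by the value contain whole neighbourhoods, sometimes several merged. Across the simulated settings, clustering the standard error on the index value gave type I error of 0.050 to 0.079. Clustering on the true neighbourhood gave 0.042 to 0.070.

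**The case against.** **The effect may be negligible.** This stands. The documents do not give the number of neighbourhoods, adolescents per neighbourhood or any intraclass correlation. Linkage by 9-digit zip code hints at small areas, though neighbourhood size is not stated. At about 3 adolescents per area the simulated error is 5% to 6%. A reader might infer that the standard error is bound to be too small; the documents support only that it may be.

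**The fault is repairable.** This stands in part. A reader might infer from the deletion that nothing can be done afterwards. That is not so, because the retained index value works as an approximate cluster variable. It has limits: the index must be kept ungrouped with many distinct values, distinct neighbourhoods with equal values are merged, and an exact neighbourhood random intercept cannot be fitted. The plan does not specify this route.

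**The order of events is not stated.** This also stands. Both sections tie deletion to derivation of the variables, and neither says that it precedes the regression. It is a fair inference, since the same risk section keeps Aim 2 recruitment data until data analysis is complete but sets no such trigger for Aim 1. It remains an inference.

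**Distance is different.** A reader might extend the result to both community-level determinants. MEASURES calculates mileage from each adolescent's own address, so it is not constant within an area and the calculation above does not apply to it.

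**Only precision is touched.** True: the argument concerns the standard error of one of six determinants, and does not by itself imply a biased estimate.

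**Conclusion.** The concern holds in a limited form. The plan tests a neighbourhood-level exposure with models that treat charts as independent, allows no design effect, and keeps no area code. The standard error of the deprivation index may therefore be too small. Under assumed values of about 3 to 15 adolescents per area and residual intraclass correlation of 0.02 to 0.05, the simulated type I error runs from about 5% (no practical fault) to about 10% (highest simulated value 10.9%). Where within the range this study falls cannot be settled from the documents.

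They do not support saying that the error is certain, that deletion makes it irreparable, or that a comparable error applies to distance. The point is still worth acting on, because an exact area grouping is easy to keep before the identifiers go and can only be approximated afterwards.

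**What to change.** 1. In DESIGN AND PROCEDURES, Procedures: Aim 1, add a step before the deletion: replace the neighbourhood code with an arbitrary area number that identifies no place, and keep that number in the analysis file. Zip codes and addresses are still deleted as planned. Make the matching change in RISK/BENEFIT ASSESSMENT.
2. In DATA ANALYSIS & STATISTICAL PLAN, Aim 1, pre-specify that the index estimate comes from the same logistic and Cox models with area-clustered robust standard errors and a small-cluster correction. The alternative is a random intercept for area in the logistic model and an area frailty in the Cox model. The distance estimate comes from the same fit.
3. Report the number of areas and of adolescents per area, so that readers can judge how much clustering there was to allow for.
4. If the identifiers have already been deleted, cluster on the ungrouped index value and describe it as an approximation.

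The cost is one extra non-identifying column, one model option, and possibly slightly wider intervals for the index. If clustering proves negligible, the results will barely change.

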## **SELECTION OF SUBJECTS**

Subjects will be identified in person at the Primary Care Pediatrics at Roxboro Road. I have gained permission from the selected clinic to conduct chart reviews and use the NCIR database to prescreen for eligible participants prior to their scheduled clinic visit. Eligibility will include: Adolescents ages 11 to 14 years who have received 1 dose of the HPV vaccine series between January 2017 and December 2017; parents as defined as the adolescent's biological mother or father, step-parents, or legal guardian; and, parents or legal guardians who self-identified as the primary caregiver of the adolescent child and most likely to make medical decisions for the adolescent. Only one parent or legal guardian and one adolescent per household will be included in the individual interviews. Exclusion criteria includes: Parents and adolescents with cognitive impairment, adolescents emancipated from their parents or legal guardian, and pregnant adolescent girls will be excluded from this study. Pregnant girls will be excluded from the study because the vaccine is not recommended for use in this population (CDC, 2016). Further, adolescents who did not receive any doses of the series are excluded since the focus of this study is to understanding barriers and facilitators to HPV vaccine completion.

## **SUBJECT RECRUITMENT AND COMPENSATION**

Recruitment will occur in-person at Duke University Primary Care Pediatrics at Roxboro Road, by phone, email or mail. Sixteen adolescents and 16 parents will be recruited from the clinic (n=32 participants). This clinic was carefully chosen for their diverse patient population of adolescents (26.4% White, 40.9% Black, 20.5% Hispanic, 2.8% Asian, and 16.7% Other). I will track race/ethnicity and gender of potential subjects to ensure participant selection is representative across all demographic groups. A request for waiver of informed consent will be submitted to the IRB to access previously collected data on adolescents' charts and the NCIR database retrospectively for Aim 1. For Aim 2, a request for waiver of informed consent will be submitted to the IRB to use adolescents' charts and the NCIR database to identify potential eligible subjects through chart reviews and to make initial contact with eligible subjects for study participation by the healthcare provider prior to obtaining consent from parents and assent from adolescents. I have gained permission to conduct chart reviews and access to use the NCIR

database to prescreen for eligible participants prior to their scheduled clinic visit. Prior to the start of the clinic day, I will provide a list of eligible participants to each healthcare provider. Clinic healthcare providers have agreed (letters of support) to provide a brief introduction of the study during clinic visits, by phone, email, and through letters sent via mail. Initial contact with eligible parents and adolescents will occur after the study has been introduced and participants have expressed their interest in the study to the healthcare provider. A brochure will be given to healthcare providers and eligible participants to provide them with additional information about the study.

**In-person recruitment.** After the study has been introduced by the healthcare provider, participants will be approached for recruitment in the patient's room and taken to a private area in the clinic to further discuss information about the study including the purpose and aims, describe participant expectations in the study, address any questions or concerns, gather their contact information, and schedule a date, time, and location to conduct the interviews at the participant's discretion and preference. The brochure and a copy of the informed consent and child assent will be provided during initial contact with participants to take home and allow them time to decide their participation in the study.

**Telephone recruitment.** I will identify eligible participants at prescreen through chart reviews and provide a list of patients to the clinic healthcare provider. At this point, the clinic healthcare provider will call the participant to briefly introduce the study using a telephone script. Eligible participant's phone numbers will be obtained from the EHR. If the participant expresses interest in the study, I will then further screen for eligibility, provide more information about the study—including participant expectations, address any questions or concerns, gather their contact information, and schedule a date, time, and location to conduct the interviews at the participant's discretion and preference. Contact information of the PI or study coordinator will also be provided to participants. A copy of the informed consent, child assent and study brochure will be provided to participants during their scheduled interviews.

**Mail recruitment.** As described above, I will identify eligible participants at prescreen through chart reviews and provide a list of patients to the clinic healthcare provider to verify that the provider has previously seen the selected patient. A letter will be sent to all eligible participants on behalf of the healthcare provider using the listed address within the EHR. The letter will contain a brief introduction of the study from the healthcare provider, the eligibility criteria, participant expectations in the study, and contact information of the PI or study coordinator (e.g. phone number and email address) to follow-up with study participation. The study brochure will also be enclosed with the letter to provide the participant with further information about the study. Per DUHS IRB policy, a two-week period from the date of the postmarked mail will be allotted to allow participants time to contact me for study participation. After the two-week period and there is no response from the eligible participant, I will contact them with study participation. Once contact has been made with participants, I will further screen for eligibility, address their questions and concerns, and schedule a date to conduct the interview at the participant's preference.

**Email recruitment.** After eligible participants are identified at prescreen through chart reviews, I will provide the list of patients to the clinic healthcare provider. An email script will be provided to healthcare providers to send out to all eligible participants. The script will include a brief introduction of the study, the eligibility criteria, participant expectations in the study, and contact information of the PI or study coordinator for participants to follow-up with study participation.

Eligible participant's emails will be obtained from the EHR and provided to the healthcare provider. As previously mentioned, after initial contact with the eligible participant has been made, I will further screen for eligibility, address their questions and concerns, and schedule an interview date and time at the participant's preference. A copy of the informed consent, child assent and study brochure will be provided to participants during their scheduled interviews.

For all recruitment methods, informed consent from parents and assent from adolescents will be obtained at the beginning of the scheduled interviews. To compensate parents and adolescents' time to participate in interviews, \$45 in cash will be provided (\$30 for parents; \$15 for adolescents).

